PK analyses randomized in the study regardless of cohort. PK blood samples will be collected on Day 1, 8, and 21 at the following timepoints after the morning dose: 15 minutes, 30 minutes, 1, 2, 3, 4, 8, and 24 hours. On Day 1 only, a pre-dose PK blood sample will be collected.

Statistical **Procedures:**

Confidential Page 14 of 102

The sample size was estimated via Monte Carlo simulations using 10,000 simulated trials.

A formal and detailed statistical data analysis plan will be prepared before database lock. The primary endpoint will be the change from Baseline to Week 4 on the PANSS total score. Formal statistical testing for comparison of the LB-102 50 mg and 75 mg treatment groups to placebo will be performed for the primary endpoint only, using appropriate procedures for multiplicity adjustment. In addition, descriptive statistics for safety, efficacy, and PK variables will be provided for all treatment groups. Shift tables for safety parameters will be prepared for appropriate categorical variables and change from Baseline and effect sizes will be calculated for efficacy measures.

The primary efficacy analysis will be performed using a Mixed Model for Repeated Measures (MMRM) using the modified Intent-to-Treat population as analysis set. The model will include treatment, site, visit, and treatment by visit interaction as categorical covariates and Baseline PANSS as continuous covariate. Within-patient correlation will be accounted for using an unstructured correlation. A similar model will be considered for continuous secondary endpoints. The response rate endpoint will be analyzed using a logistic regression model with treatment as categorical covariate and Baseline PANSS total score as continuous covariate.

Safety: Safety variables to be examined in this study will include AEs, physical examinations, vital signs, body weight, BMI (derived programmatically from body weight and height measurements), waist circumference, clinical laboratory tests (hematology, serum chemistry [including prolactin]), urinalysis, pregnancy tests, PT, aPTT, INR, HbA1c, cortisol, ACTH, TSH, total cholesterol, triglycerides, HDL, and LDL, ECGs, and an evaluation of extrapyramidal symptoms using the SAS, AIMS, and BARS. The C-SSRS will be used to assess and classify reported suicidal behavior.

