10.4.4.2 Primary Efficacy Endpoint

The primary endpoint is the change from Baseline to Week 4 in the PANSS total score. The null and alternative hypothesis for each dose level are as follows:

H₀: the difference in the change from Baseline to Week 4 in the PANSS total score between LB-102 active treatment and placebo is equal to 0;

H₁: the difference in the change from Baseline to Week 4 in the PANSS total score between LB-102 active treatment and placebo is different from 0.

All efficacy endpoints will be analyzed for the mITT Analysis Set, and the primary endpoint will also be analyzed for the PP Analysis Set.

Principal Analysis

In line with the estimand definition, all data collected after the occurrence of an ICE will be included in the primary efficacy analysis. As a primary analysis, all missing data due to study discontinuation for lack of efficacy or drug-related AEs will be imputed assuming a Missing Not At Random (MNAR) mechanism and assuming that after withdrawal the subjects revert to the distribution of the worst PANSS score values observed up to time of discontinuation, whereas missing data due to discontinuation for any other reason, will be imputed under a Missing At Random (MAR) assumption using a Multiple Imputation (MI) approach.

The primary efficacy endpoint (change from Baseline to Week 4 on the PANSS total score) will be analyzed using a Mixed Model for Repeated Measures (MMRM) approach, including site, visit, treatment, and their interaction as categorical covariates and Baseline PANSS as continuous covariates. Within -patient correlation across repeated measures will be accounted for by using an unstructured correlation, or the best fit structure should an unstructured matrix cause convergence issues. The differences between active treatment groups and placebo at Week 4 will be estimated alongside confidence intervals (CIs) and *P* values. The model will be fit separately for each imputed dataset and results pooled using Rubin's rules to derive one treatment effect estimate.

This analysis will be performed for the mITT and repeated for the PP Analysis Set. Should the mITT and ITT differ substantially (e.g., by at least 10%) the primary analysis will be performed for the ITT and the mITT only be regarded as supportive information.

Confidential Page 82 of 102

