### 3 SAMPLE SIZE

[REDACTED] patients will be randomized in a 3:3:3:1 ratio to placebo, LB-102 50 mg QD, LB-102 75 mg QD, or LB-102 100 mg QD, respectively, with [REDACTED] patients randomized to each of the first 3 arms and [REDACTED] to the last one (LB-102 100 mg). This will ensure at least 85% power at a 2-sided 5% significance level to detect a treatment difference on the primary endpoint of 8 between either LB-102 50 mg or 75 mg and placebo QD, assuming a common SD of 18, an overall drop-out rate of 25% and a Hochberg procedure to adjust for multiplicity. The sample size was estimated via Monte Carlo simulations using 10,000 simulated trials.

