* Set Week 4 = WORST4 for missing data;

data step5b;
set step5a;
week_4 = ifn(missing(week_4), worst4, week_4);
run;

```

Upon completion of the above imputation steps, the change from baseline in the PANSS score will be derived and used in the statistical modelling. To such aim, a MMRM will be fit for each imputed dataset, including pooled study site, visit, treatment and treatment by visit interaction as categorical effects and Baseline PANSS total score as continuous covariate and the change from Baseline in the PANSS total score at 1, 2, 3 and 4 weeks after baseline as response. Correlation between repeated observations within a patient will be accounted for via an unstructured correlation matrix, however, should this structure lead to convergence issues, the following decreasingly complex alternative structures will be fit in turn until the model converges: Toeplitz, first-order autoregressive, and compound symmetry. The assessment of model convergence will be done prior to unblinding. The LS means for change from Baseline to all post-Baseline timepoints in the PANSS total score and their differences between the active treatment arms (50 and 75 mg) and placebo will be estimated for each imputed dataset. Model assumptions will be examined graphically for a random selection of 10% imputations (i.e. 10) via inspection of conditional residuals scatterplots (residuals vs predicted values), quantile-quantile plots and histograms. Should any substantial violation be observed, non-parametric analyses (e.g. Wilcoxon rank-sum test) will be adopted, and this decision will be documented based on blinded data prior to database lock. This model will be fit using the example SAS code below:

```

ods output estimates = est LMeans = lsm diff = diff;
proc mixed data =  plots (only) = studentpanel(marginal);
by _imputation_;
class subjid trt01pn avisitn siteid;
model chg = trt01pn siteid avisitn trt01pn*avisitn base / ddfm = kr;
repeated avisitn / type = un subject = subjid;
lsmeans trt01pn*avisitn / diff cl;
run;

```

The model estimates (LS means and their differences between treatment arms) will be pooled using Rubin's combination rules to incorporate the between-imputation with the within-imputation variability and to obtain one single point and interval treatment effect estimate for each active arm using the PROC MIANALYZE procedure. The below sample SAS code implements the pooling across imputations:

```

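### The primary MMRM has no baseline-by-visit term, so the Week 4 effect is adjusted with one baseline slope pooled over Weeks 1–4, which may cost some precision at Week 4

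*SAP*

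**What the plan says.** The SAP code for the primary model is "model chg = trt01pn siteid avisitn trt01pn*avisitn base / ddfm = kr", with "repeated avisitn / type = un subject = subjid". The SAP text describes the same terms: "treatment by visit interaction as categorical effects and Baseline PANSS total score as continuous covariate". The response is "the change from Baseline in the PANSS total score at 1, 2, 3 and 4 weeks after baseline as response", fitted to data already completed by multiple imputation. If the unstructured matrix fails to converge, the fallbacks are "Toeplitz, first-order autoregressive, and compound symmetry".

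The protocol matches. Its synopsis has "visit, and treatment by visit interaction as categorical covariates and Baseline PANSS as continuous covariate". Its section 10.4.4.2 has "including site, visit, treatment, and their interaction as categorical covariates and Baseline PANSS as continuous covariates", where the interaction belongs to the categorical terms and baseline stands apart. None of the four places lets the baseline slope differ by visit.

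**The concern.** Treatment means are free at every visit, and so are the variances under the unstructured matrix. Only the relation between baseline and change is held constant. The primary test uses one visit, Week 4, but the slope that adjusts it is estimated from all four. A slope that suits the early visits can be wrong for Week 4, in which case part of the baseline adjustment is given up at the only formally tested time point. At stake is precision, and so a little power, not validity.

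**Working it through.** **The plan's own figure.** SAP section 3 states "This will ensure at least 85% power at a 2-sided 5% significance level to detect a treatment difference on the primary endpoint of 8", with SD 18, 25% drop-out and a Hochberg adjustment. The number per arm is blacked out, so the power cannot be reproduced. The stated inputs imply these evaluable numbers per arm, divided by 0.75 to give randomized numbers:
- at least one dose to succeed: 77, so 103 randomized
- a given dose when both work: 95, so 127 randomized
- both doses to succeed: 111, so 148 randomized

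**Formulas.** The data are complete after imputation and treatment-by-visit is saturated. Ignoring site:
- Common slope: g = w₁g₁ + w₂g₂ + w₃g₃ + w₄g₄, where gₜ is the slope at Week t, w = V⁻¹1/(1′V⁻¹1) and V is the residual covariance over the four visits.
- Week 4 effect: difference in Week 4 change − g × difference in baseline.
- Extra Week 4 variance, as a proportion: (g₄ − g)² × SD_base² / SD₄².
- Share of the adjustment gain lost: (1 − g/g₄)².

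**Inputs.** From the SAP: four visits and SD 18, taken here as the Week 4 residual SD. Assumed, because the documents are silent: baseline SD 9.5, the visit SDs and correlations below, and g₄ from −0.2 to −0.5 with the slope rising linearly from 30% of g₄ at Week 1.

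**What is at stake in total.** Dropping baseline adjustment altogether would add g₄² × 9.5²/18². That is 0.04 × 0.2785 = 1.1% at g₄ = −0.2 and 0.25 × 0.2785 = 7.0% at g₄ = −0.5.

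**One case in full.** Take SDs 9/13/16/18, autoregressive correlation 0.8 and g₄ = −0.5.
- Slopes: −0.15, −0.267, −0.383, −0.5.
- Weights: 1.19, −0.21, −0.05, 0.07.
- g = −0.138, which is 0.28 of g₄.
- Extra variance: (0.362)² × 0.2785 = 3.7%.

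**Range.** Three correlations per row: 0.6, 0.7, 0.8.

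| SDs, Weeks 1–4 | Correlation | Weight on Week 1 | g/g₄ | Share of gain lost | Extra Week 4 variance |
|---|---|---|---|---|---|
| 9/13/16/18 | autoregressive | 0.84, 0.98, 1.19 | 0.40, 0.35, 0.28 | 36%, 42%, 53% | 0.4–3.7% |
| 9/13/16/18 | exchangeable | 0.98, 1.14, 1.35 | 0.25, 0.16, 0.04 | 57%, 71%, 92% | 0.6–6.4% |
| 13/15/17/18 | autoregressive | 0.57, 0.66, 0.80 | 0.52, 0.49, 0.435 | 23%, 26%, 32% | 0.25–2.2% |
| 13/15/17/18 | exchangeable | 0.63, 0.76, 1.00 | 0.41, 0.32, 0.17 | 35%, 46%, 68% | 0.4–4.8% |
| 18 throughout | autoregressive | 0.36, 0.38, 0.42 | 0.65 | 12% | 0.1–0.9% |
| 18 throughout | exchangeable | 0.25 | 0.65 | 12% | 0.1–0.9% |

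More than half the gain is lost only when g/g₄ is below 1 − √0.5 = 0.29. A constant slope loses nothing. A more extreme set (baseline SD 12, slopes from −0.2 at Week 1 to −0.6 at Week 4) reaches 8.5%.

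**Simulation.** With 1,500 trials and 100 per arm, the empirical SD of the Week 4 effect (common against visit-specific slope) was:
- 2.66 against 2.60 (9/13/16/18, autoregressive 0.8, slopes −0.05 to −0.40)
- 2.60 against 2.54 (same covariance, slopes −0.2 to −0.6)
- 2.59 against 2.58 (13/15/17/18, Toeplitz, slopes −0.15 to −0.40)

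No material bias appeared (Monte Carlo error about 0.07). None is expected, since randomization makes the mean baseline difference zero whatever g is.

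**Power.** At an assumed 96 evaluable per arm, power is 86.9% at two-sided 0.05. With 1%, 2%, 3% and 5% extra variance it falls to 86.5%, 86.2%, 85.9% and 85.2%, a loss of 0.3 to 1.7 points.

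**The case against.** The best defence is that the model is prespecified, identical in both documents and valid. The response is already a change score, so baseline is subtracted whatever the slope, and only a refinement is missing. That stands: there is no contradiction or bias, and a modelling preference is a fair description.

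A reader might infer that an unstructured covariance makes the common slope essentially the Week 1 slope. It does not. Week 1 dominance comes from the assumed growth in variance. With equal SDs the Week 1 weight is at most 0.42, and the fallback structures, as named, have constant variance.

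A reader might also infer that Week 4 loses most of its baseline adjustment. Under the steepest SDs with autoregressive correlation the loss is 36–53%. Across the table it runs from 12% to 92%, on inputs that the documents do not contain.

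Nor is the rise in slope over time a documented fact. It is plausible for change scores, but it is an assumption here.

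Two further inferences fail. The imputation code in SAP 5.11.2 gives each week its own regression on baseline, so it is richer than the analysis model. That is the usual safe direction and not a fault. And the arithmetic covers PANSS total only, so it shows no loss for CGI-S, the subscales or the Marder factors.

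**Conclusion.** The point holds as a small, conditional gain in precision. The omission is certain, but its cost is not. Under the main assumptions (baseline SD 9.5, Week 4 SD 18, slope rising from 30% at Week 1 to a Week 4 value of −0.2 to −0.5), Week 4 variance is about 0.1–4% larger with autoregressive-type correlation. It is up to about 6% larger with strong exchangeable correlation. In power, that is usually within 2 points. If the slope is the same at all visits, nothing is lost and the extra term gains nothing. The documents do not support calling this an error, a bias or the loss of most of the adjustment. It is worth doing because it is cheap and acts at the one formally tested time point.

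**What to change.** - Add `base*avisitn` to the MODEL statement in SAP 5.11.2, keeping the main effect, and name the baseline-by-visit interaction in the text. The LSMEANS statement can stay: baseline does not interact with treatment, so treatment differences at a visit do not depend on the baseline value.
- Carry the term to the sensitivity analyses in 5.11.3, which reuse this model, and, for consistency, to the similar secondary MMRMs in 5.11.5.1 to 5.11.5.4 with each endpoint's own baseline. The subgroup models in 5.11.4.1 inherit it by reference.
- List it in SAP section 8, because both protocol descriptions specify the model without the term. Approve it before database lock, as SAP section 5 requires.

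The cost is 3 degrees of freedom (four slopes instead of one), a short SAP amendment, and a negligible loss of precision if slopes do not differ by visit.

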### 5.11.3 Sensitivity Analysis

#### 5.11.3.1 Sensitivity Analysis #1: Re-mapped Early Termination Assessments

The primary analysis will be repeated but including PANNS values obtained during early termination assessments in the analysis, i.e. by re-mapping them to the analysis windows described in Section 5.2.4 in place of PANSS collected at the planned visit mapped to the same analysis window. Similar displays and quantities to the primary analysis will be provided.

#### 5.11.3.2 Sensitivity Analysis #2: Tipping-Point Analysis

As an additional sensitivity analysis, all missing PANSS total score values that have been imputed using a MAR approach as described in Section 5.11.2 will be imputed under a MNAR mechanism using a tipping-point approach, i.e. by adding a treatment-specific constant shift to the MAR-imputed values in order to assess how severe a MAR violation needs to be for the results to change, i.e. for the results of the primary analysis to no longer be deemed as statistically significant (that is, for neither of the 50 or 75 mg arms to meet the thresholds described in Section 5.11.7). The following set of shifts values will be initially considered: 2, 4, 6, 8 and 10, with the potential combinations across arms described in Table 5 below.

**Table 5.** Shift combinations for tipping point analysis

		LB-102 Arms Shift				
		2	4	6	8	10
Placebo Arm Shift	2	x	x	x	x	x
	4		x	x	x	x
	6			x	x	x
	8				x	x
	10					x

The lower triangle will not be investigated because it would be associated with scenarios where the penalties are larger for the Placebo arm, thus unlikely to reveal any negative change in study results.

The same MMRM as considered for the primary analysis will then be fit for each multiply imputed dataset by shift pair, and results pooled to obtain, for every set of shift values, one treatment effect for each active arm. This analysis will only be performed if at least one active arm's primary analysis result was deemed as statistically significant under the multiple testing strategy defined in Section 5.11.7. The first combination of shifts where significance can't be concluded for any active arm (using the same multiplicity approach as for the primary analysis) will be identified as the tipping-point, and its plausibility evaluated. For this purpose, the shifts combinations will be ordered column-wise, e.g. assuming that a combination of placebo/active shifts of 8-8 is more 'plausible' than a 2-10. If no tipping-point is identified using the above combinations, extra shifts will be evaluated by shifting the values for LB-102 arms by a value of 12 and then, within this, exploring shifts from 2 to 12 for Placebo, and so on until a shift is identified or all MAR imputed data have been imputed to maximum PANSS total score possible (= 210).

For each of the above pairs, the treatment effects and associated p-values for both arms will be presented, alongside results of the multiplicity adjustment procedure described in Section 5.11.7.

### 5.11.3.3 Sensitivity Analysis #3: Reference-based Imputation

For this sensitivity analysis, all missing data due to drop-out will be imputed using a pattern-mixture model, whereby data will be imputed only using data from patients with no missing data from the Placebo (reference) arm, i.e. assuming that all patients randomized to an active arm had had a profile on the primary endpoint similar to that of patients randomized to Placebo. To achieve this, first non-monotone missing data on the PANSS will be imputed under a MAR mechanism using a Markov-Chain Monte Carlo (MCMC) approach, using the below sample SAS code:

```
proc mi data =  nimpute = 100 seed = 99 out = <output-dataset>
minimum = 30 maximum = 210;
by trt01pn;
var base d8 d15 d21 d28;
```

```
mcmc chain = multiple impute = monotone initial = em prior = jeffreys;
run;
```

Where the variables included in the VAR statement represent the PANSS total score at the relevant timepoints throughout the study, the IMPUTE = MONOTONE option means that missing data points will be imputed to achieve a monotone missing data pattern, and the PRIOR = JEFFREYS option specifies a non-informative prior for the imputation process, so that the posterior distribution used for the imputation is largely affected by the observed data themselves. These imputed datasets will then be imputed using the copy-reference method via the below SAS code:

```
proc mi data =  nimpute = 1 seed = 99 out = <output-dataset>
minimum = 30 maximum = 210;
by _imputation_;
class trt01p;
var baseline d8 d15 d21 d28;
fcs nbiter = 1000 regpmm(baseline d8 d15 d21 d28);
mnar model(baseline d8 d15 d21 d28/ modelobs = (trt01p = 'Placebo'));
run;
```

The BY statement will ensure that the above MNAR imputation is performed separately for each MAR-imputed dataset as generated by the previous imputation step. The same MMRM will then be fit to all imputed datasets and results pooled across imputations, using the SAS code described in Section 5.11.2 for both the analysis and the pooling, and thus reporting similar quantities from the model.

## 5.11.4 Exploratory Analysis

### 5.11.4.1 Subgroup analysis

The primary analysis model (MMRM) described in Section 5.11.2 will be used for the purposes of subgroups analyses, with no prior imputation for missing data. For each subgroup variable stratum the model will be fit and estimates of LS means and their differences over time will be provided, alongside 95% CIs as well as, for differences, p-values (only for descriptive purposes). The following subgroups will be explored:

- BMI at Baseline:  $\leq 25 \text{ kg/m}^2$ ,  $25 \text{ to } 30 \text{ kg/m}^2$ ,  $\geq 30 \text{ kg/m}^2$
- Baseline PANSS (disease severity):  $\leq 95$ ,  $> 95$

The results for these subgroups analysis will also be displayed in a forest plot (Week 4 only).

### 5.11.4.2 Site Effect

Descriptive summaries of observed and change from baseline values for the PANSS total score will be provided by study site (regardless of pooling), but no statistical analysis will be performed.

## 5.11.5 Secondary Endpoints

All secondary endpoints will be analyzed on the ITT analysis set. As described in Section 5.11.2, should the ITT and mITT analysis sets overlap substantially, secondary endpoints will only be analyzed on the mITT analysis set.

#### **5.11.5.1 Change from Baseline to Week 4 in the CGI-S score**

The change from Baseline in the CGI-S score will be analyzed using a similar MMRM as the one for the primary endpoint, replacing baseline CGI-S as covariate in the model. Similar quantities (LS means and their differences, with 95% CIs and p-values) will be presented. Descriptive summaries of observed and change from Baseline values will be presented for all treatment arms.

CGI-S response, defined as a CGI-S score  $\leq 3$ , will also be analyzed separately for each time-point, categorizing any patient with missing data as a non-responder. The number of patients meeting this definition will be summarized descriptively on the mITT analysis set with counts and percentages, including approximate Wald-type 95% CI (with a continuity correction). The difference between treatment arms in the above defined responder rate will be analyzed by reporting the estimated difference in proportions alongside its 95% Wald-type 95% CI with a continuity correction as well as the  $P$ -value derived from Fisher's exact test (using a Monte Carlo approximation to deal with the large sample size). Example SAS code is provided below:

```
ods output RiskDiffCol2 = diff FishersExact = fisher;
proc freq data = ;
  by atptn;
  tables trt01pn*avalc / riskdiff (column = 2 cl = (wald(correct))) chisq;
  exact fisher / mc seed = 123;
run;
```

For the derivation of the exact p-value, it is assumed that the 2x2 table for each visit has the following form:

Treatment	Non-Response	Response
LB-102	a	b
Placebo	c	d

Under the above structure, Fisher's test as implemented in PROC FREQ is defined based on the value  $a$  in the first row/column and the associated one-sided p-values support different alternative hypotheses (the null being that of independence between row and columns):

- Left-sided p-value: supports the alternative that the probability of a patient treated with LB-102 of being a non-responder is smaller than what would be expected under the independence null;
- Right-sided p-value: supports the alternative that the probability of a patient treated with LB-102 of being a non-responder is larger than what would be expected under the independence null.

Since the hypothesis we're interested in is that patients treated with LB-102 are more likely to be responders than non-responder, a small left-sided p-value supports this hypothesis and as such this is the p-value that will be reported in the table. All CGI-S data will also be listed.

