## SAP Amendments before database lock

Version	Issue Date	Section	Revision / Addition	Rationale
1.0	24-Nov-2023	-	-	First final version issued
2.0	14-Dec-2023	2.3	Changed the relevant analysis set for the estimands	ITT will be used as primary analysis set, but a caveat has been added to move to the mITT if this substantially overlaps with the ITT.
		5.1	Exclusion of the Per-Protocol Analysis Set	The Per-Protocol Analysis Set is not useful from a regulatory standpoint and provides results that are difficult to interpret in the best of cases, so it has been agreed to remove it.
		5.2.4	Clarification of ET assessments remapping	The rules for remapping assessments performed during an ET visit have been clarified, and some alternative options have been proposed.
3.0	17-May-2024	5.2	Derivation of questionnaires scores	The definition and rules for scoring study questionnaires have been added.
		5.3	Added details for PK summary statistics.	Since PK is usually summarized with geometric summaries details for these have been added.
		5.11.3	The structure and content of the sensitivity analysis section was revised	All sensitivity analyses are now described in this section, and the rules to identify the tipping-point have been clarified to account for the use of the Hochberg multiplicity adjustment across doses.
		5.12	Analyses of PK endpoints have been detailed more clearly.	The scope of reporting for PK parameters has been clarified and an analysis for dose-proportionality

				has also been added in line with protocol requirements.
4.0	20-November-2024	5.11.2	Adjusted the MNAR imputation description to remove any mention of post-ICE data imputation and the SAS sample codes have been adjusted for clarity	As part of the primary estimand, data collected after ICE is retained in the statistical analysis.
		5.11.3.3	Clarified that no imputation is done with regard to data collected after ICES.	As part of the primary estimand, data collected after ICE is retained in the statistical analysis.
		5.11.5.1	The analysis method for the CGI-S response endpoint has been adjusted to reflect computational issues occurred during the dry-run.	Exact calculations are computationally intensive with this size and give rise to log issues, so an alternative has been pursued.

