In addition to the above summary tables, relative risks for the occurrence of any AE (i.e., at least 1 AE) during the course of the study as well as for each system organ class/preferred term will be estimated for each LB-102 dose vs placebo via a log-binomial regression model. For such analysis, the binary indicator for the presence of a given system organ class/preferred term (or any AE) will be used as response and the treatment group will be the only covariate, whose estimated regression coefficient will be exponentiated to return the associated relative risk, alongside their 95% CI and p-values. To such aim, the following sample SAS code will be used:

```
ods output estimates = rr;
proc genmod data =  descending;
  by aedecod aeterm;
  class subjid trt01an;
  model ae_binary = trt01an / dist = binomial link = log;
  estimate 'RR LB-102 50 mg vs. Placebo' trt01pn 1 0 0 -1 / exp alpha = 0.05;
  estimate 'RR LB-102 75 mg vs. Placebo' trt01pn 0 1 0 -1 / exp alpha = 0.05;
  estimate 'RR LB-102 100 mg vs. Placebo' trt01pn 0 0 1 -1 / exp alpha = 0.05;
run;
```

The above code assumes that the TRT01PN variable is ordered such that placebo is the last arm (i.e. TRT01PN = 4) and the others are sorted in ascending order, lowest to highest, and that AEDECOD and AETERM are the system organ class and preferred term variables, respectively.

All AEs will be listed.

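### The CGI-S responder code in SAP 5.11.5.1 is not restricted to one dose and placebo, as its own two-by-two table requires, and the Monte Carlo Fisher p-value is unnecessary for such a table

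*SAP*

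**What the plan says.** SAP 5.11.5.1 defines CGI-S response as a score of 3 or less and analyses it visit by visit, counting missing data as non-response. The effect is given by "reporting the estimated difference in proportions alongside its 95% Wald-type 95% CI with a continuity correction". The p-value comes from Fisher's exact test, "using a Monte Carlo approximation to deal with the large sample size". The SAP amendment table gives the reason for the change: "Exact calculations are computationally intensive with this size and give rise to log issues, so an alternative has been pursued".

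The example code has one BY variable, the timepoint. Its table request is "tables trt01pn*avalc / riskdiff (column = 2 cl = (wald(correct))) chisq", followed by "exact fisher / mc seed = 123". No number of Monte Carlo samples is given, and no statement selects a dose.

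The text after the code says that "it is assumed that the 2x2 table for each visit has the following form" and shows two rows, LB-102 and Placebo. It concludes that "a small left-sided p-value supports this hypothesis and as such this is the p-value that will be reported in the table".

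The treatment variable has four levels. SAP 5.3 lists four treatment columns, and SAP 5.13.1 says of the adverse event code: "The above code assumes that the TRT01PN variable is ordered such that placebo is the last arm (i.e. TRT01PN = 4").

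**The concern.** The text and the code describe different tables. A left-sided Fisher p-value and a single difference in proportions exist only for a two-row table. The code, given all four arms, builds a four-row table. On that table Fisher's test asks whether response differs anywhere among the arms, has no direction, and comes with no single risk difference.

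The text also leaves the LB-102 row undefined. Speaking of the difference between treatment arms suggests separate doses, but no dose is named and pooling is not ruled out.

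The reason given for Monte Carlo does not fit the two-by-two table either. There the exact p-value is a short sum, so simulation replaces a number that can be had exactly with one that carries random error. At stake is whether the tabulated p-value answers the dose-versus-placebo question and can be recovered exactly by a second programmer.

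**Working it through.** **Plausible arm size.** The number of patients is redacted, so the stated power of at least 85% cannot be reproduced. The other sizing inputs (SAP 3: difference 8, SD 18, drop-out 25%, Hochberg) imply a range. For one comparison, n = 2(z₁₋α/₂ + z₀.₈₅)²(18/8)²:

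- two-sided α = 0.05: 2 × (1.960 + 1.036)² × 5.0625 gives 91 completers; 91/0.75 gives 122 randomized per arm
- two-sided α = 0.025: 2 × (2.241 + 1.036)² × 5.0625 gives 109 completers; 109/0.75 gives 146 per arm

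A Hochberg simulation with a shared placebo arm and both doses effective (200,000 trials) reaches 85% for at least one dose at about 78 completers (104 randomized) per arm, and for a given dose at about 95 to 96 (127 to 128). Plausible arms are therefore about 104 to 146 randomized. The check below uses 80, 108 and 150.

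**Exact two-by-two test.** Assumed response is 40% on drug and 25% on placebo. With n per arm, K non-responders in total and a non-responders on drug:

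- P(a) = C(n, a) C(n, K − a) / C(2n, K)
- the left-sided p-value sums P from the smallest possible a up to the observed one
- number of possible tables = min(n, K) − max(0, K − n) + 1

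At n = 108, with 65 and 81 non-responders, K = 146 and the count is 108 − 38 + 1 = 71.

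| n per arm | Non-responders, drug / placebo | Possible tables | Exact left p | Exact two-sided p | One Monte Carlo left p (10,000 samples) |
|---|---|---|---|---|---|
| 80 | 48 / 60 | 53 | 0.0314 | 0.0628 | 0.0288 |
| 108 | 65 / 81 | 71 | 0.0144 | 0.0288 | 0.0160 |
| 150 | 90 / 112 | 99 | 0.0048 | 0.0096 | 0.0055 |

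Each exact calculation took about 3 ms.

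**Monte Carlo error.** With 10,000 samples (an assumption), the standard error at p = 0.05 is √(0.05 × 0.95 / 10,000) = 0.0022. The 95% half-width is 1.96 × 0.0022 = 0.0043, and the 99% half-width is 0.0056. A fixed seed makes this error repeatable; it does not remove it.

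**The four-row table.** Assume 108, 108, 108 and 36 patients on 50 mg, 75 mg, placebo and 100 mg, following the 3:3:3:1 allocation. The global p-value sums the probabilities of all tables no more likely than the observed one.

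| Non-responders (50 mg / 75 mg / placebo / 100 mg) | Possible tables | Global p | 50 mg v placebo, exact two-sided | 75 mg v placebo, exact two-sided |
|---|---|---|---|---|
| 65 / 65 / 81 / 22 | 224,004 | 0.062 | 0.029 | 0.029 |
| 65 / 81 / 81 / 27 | 150,294 | 0.054 | 0.029 | 1.000 |

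In the first scenario the planned difference for 50 mg is 43/108 − 27/108 = 0.148. The four-row analysis returns neither this figure nor the left-sided p-value of 0.014.

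**The case against.** The code is labelled an example and reads a placeholder dataset, which may already be cut to one dose and placebo. The text states the two-by-two assumption outright. The SAP's sample code is skeletal elsewhere too: the frequency code for PANSS response in 5.11.5.5 also crosses treatment with response unfiltered. A literal four-arm run would lack both quantities the text asks for, and Table 14.2.2.1.2 is to be independently programmed by a statistician, so the mismatch should be noticed.

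All of this stands. A reader might infer that the SAP plans a global four-arm test; the documents do not support that. What remains is that the restriction is nowhere written, although SAP 5.13.1 does code each dose-versus-placebo contrast. Pre-filtering would cure the table, but on the resulting two-by-two table sample size is no reason for Monte Carlo.

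A reader might also infer that an exact test on a four-arm table caused the dry-run trouble. The amendment table does not say which exact calculation was burdensome; exact confidence limits are another candidate. Full enumeration of the four-row tables above took under a second, so the arithmetic does not settle it.

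Finally, no decision at 0.05 rests on this p-value. The protocol synopsis confines formal testing to the primary endpoint, the Hochberg procedure in SAP 5.11.7 covers only that endpoint, and CGI-S response is not among the secondary endpoints listed in SAP 2.2.2. That limits the importance of the point but does not remove the inconsistency.

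**Conclusion.** The point holds as a mismatch between text and example code, plus an unnecessary approximation. As written, the code does not restrict to one dose and placebo. Run on all four levels, it cannot deliver the left-sided p-value or the difference in proportions, and its global p-value can differ materially from the pairwise ones (0.062 against 0.029 in the assumed example). Separately, Monte Carlo is not needed for a two-by-two Fisher test at any arm size this trial could plausibly have, and it adds an error of about ±0.004 at p = 0.05.

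These sizes rest on assumed arm sizes, response rates and a 10,000-sample Monte Carlo run, none of which the documents give. The conclusion that the exact test is trivial does not depend on the particular values in the range checked. The impact is limited to a supportive responder p-value; the primary analysis is untouched. Whether that p-value should be one-sided is a different question.

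**What to change.** In SAP 5.11.5.1, run PROC FREQ by visit for each pair: 50 mg, 75 mg and 100 mg, each against placebo. Name the dose in the two-by-two table so that the LB-102 row cannot be read as pooled. Remove the `mc` option and its seed, report the exact Fisher p-value, and delete the justification by sample size.

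The cost is a WHERE clause or a loop over three pairs and one sentence of text. No new data or outputs are needed, and run time is negligible.
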